8.3.4 IBS Severity Score System

Patients will be asked to complete 5 questions regarding the severity of their IBS. Each of the 5 questions generate a maximum score of 100, leading to a total possible score of 500.

8.4 Safety and Other Assessments

8.4.1 Adverse Events and Serious Adverse Events

See [Section 8.5](#).

8.4.2 Physical Examinations

A complete physical examination (PE) will be performed at Screening. At a minimum, a targeted PE will be performed at the timepoints specified in the Schedule of Activities ([Section 1.3](#)) with additional symptom-directed examination performed as clinically indicated. Any clinically significant PE finding noted at Screening will be recorded as medical history in the source document. Any clinically significant PE finding noted at after enrollment will be reviewed for reporting as an AE (see [Section 8.5](#)).

A complete PE will include, at a minimum, assessment of the cardiovascular, respiratory, GI, and neurological systems. A targeted PE will include, at a minimum, assessments of the lungs, cardiovascular system, and abdomen (liver and spleen).

Height and weight will also be measured and BMI will be calculated and the data recorded at the timepoints specified in the Schedule of Activities ([Section 1.3](#)).

Investigators should pay special attention to clinical signs related to previous serious illnesses.

8.4.3 Vital Signs

At the timepoints specified in the Schedule of Activities ([Section 1.3](#)) and before any blood sample collection, vital signs will be measured in a supine position after 5 minutes rest and will include oral temperature, systolic and diastolic blood pressure, pulse, and

respiratory rate. Any clinically significant abnormal vital sign value will be recorded as an AE (see [Section 8.5](#)).

8.4.4 Electrocardiograms

Single 12-lead ECGs will be performed at the timepoints specified in the Schedule of Activities ([Section 1.3](#)) and before any blood sample collection. Electrocardiogram interval measurements and interpretation (normal, abnormal not clinically significant, abnormal clinically significant) will be recorded in the source document. Any clinically significant change in ECG interpretation will be recorded as an AE (see [Section 8.5](#)).

8.4.5 Clinical Safety Laboratory Assessments

See [Appendix 1](#) for the list of clinical laboratory tests to be performed and to the Schedule of Activities ([Section 1.3](#)) for the timing and frequency.

The Investigator must review the laboratory report, document this review, and record in the AE section of the CRF any clinically relevant changes occurring during the study. The laboratory reports must be filed with the source documents. Clinically significant abnormal laboratory findings are those that are not associated with the underlying disease, unless judged by the Investigator to be more severe than expected for the patient's condition.

All laboratory tests with values considered clinically significantly abnormal during participation in the study should be repeated until the values return to normal or baseline or are no longer considered clinically significant by the Investigator or Medical Monitor. If such values do not return to normal/baseline within a period of time judged reasonable by the Investigator, the etiology should be identified and the sponsor notified.

All protocol-required laboratory assessments, as defined in [Appendix 1](#), must be conducted in accordance with the laboratory manual and the Schedule of Activities.

If laboratory values from non-protocol-specified laboratory assessments performed at the institution's local laboratory require a change in patient management or are considered clinically significant by the Investigator (e.g., SAE, or AE, or dose modification), then the results must be recorded in the CRF.

8.5 Adverse Events and Serious Adverse Events

Adverse events will be reported by the patient (or, when appropriate, by a caregiver, surrogate, or the patient's legally authorized representative).

The Investigator and any qualified designees are responsible for detecting and documenting events that meet the definition of an AE or SAE and are responsible for following all AEs.

8.5.1 Definition of Adverse Events

An AE is any untoward medical occurrence in a patient or clinical study participant, temporally associated with the use of investigational product, whether or not considered related to the investigational product. An AE can therefore be any unfavorable and unintended sign (including an abnormal laboratory finding), symptom, or disease (new or exacerbated) temporally associated with the use of investigational product.

8.5.2 Events of Special Interest

Not applicable.

8.5.3 Definition of Serious Adverse Events

If an event is not an AE per definition above, then it cannot be an SAE even if serious conditions are met (e.g., hospitalization for signs/symptoms of the disease under study, death because of progression of disease).

A SAE is defined as any untoward medical occurrence that, at any dose:

- Results in death;
- Is life threatening;

The term 'life threatening' in the definition of 'serious' refers to an event in which the patient was at risk of death at the time of the event. It does not refer to an event, which hypothetically might have caused death, if it were more severe.

- Requires inpatient hospitalization or prolongation of existing hospitalization;

In general, hospitalization signifies that the subject or patient has been detained (usually involving at least an overnight stay) at the hospital or emergency ward for observation and/or treatment that would not have been appropriate in the physician's office or outpatient setting. Complications that occur during hospitalization are AEs. If a complication prolongs hospitalization or fulfills any other serious criteria, the event is serious. When in doubt as to whether "hospitalization" occurred or was necessary, the AE should be considered serious.

Hospitalization for elective treatment of a pre-existing condition that did not worsen from baseline is not considered an AE;

- Results in persistent disability/incapacity;

The term disability means a substantial disruption of a person's ability to conduct normal life functions. This definition is not intended to include experiences of relatively minor medical significance such as uncomplicated headache, nausea,

vomiting, diarrhea, influenza, and accidental trauma (e.g., sprained ankle) that may interfere with or prevent everyday life functions but do not constitute a substantial disruption.

- Is a congenital anomaly/birth defect.

Medical or scientific judgment should be exercised when deciding if SAE reporting is appropriate in other situations such as important medical events that may not be immediately life threatening or result in death or hospitalization, but may jeopardize the patient or may require medical or surgical intervention to prevent any of the other outcomes listed in the above definition. These events should usually be considered serious. Examples of such events include invasive or malignant cancers, intensive treatment in an emergency room or at home for allergic bronchospasm, blood dyscrasias or convulsions that do not result in hospitalization, or development of drug dependency or drug abuse.

8.5.4 Classification of an Adverse Event

8.5.4.1 Assessment of Severity

The Investigator will make an assessment of severity for each AE and SAE reported during the study and assign it to 1 of the following categories:

- Mild: An event that is easily tolerated by the patient, causing minimal discomfort and not interfering with everyday activities;
- Moderate: An event that causes sufficient discomfort and interferes with normal everyday activities;
- Severe: An event that prevents normal everyday activities. An AE that is assessed as severe should not be confused with a SAE. Severe is a category utilized for rating the intensity of an event; and both AEs and SAEs can be assessed as severe.

An event is defined as 'serious' when it meets at least 1 of the predefined outcomes as described in the definition of an SAE, NOT when it is rated as severe.

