3 OBJECTIVES AND ENDPOINTS

OBJECTIVES	ENDPOINTS
Primary	

 To evaluate in patients with IBS-D the abdominal pain response to BOS-589 after 4 weeks of treatment, relative to placebo (PBO). To evaluate the overall safety and tolerability of BOS-589 in the treatment of IBS-D during 4 weeks of treatment, relative to PBO. 	
 24-hour worst abdominal pain scores (WAP) at Day 29 compared to baseline (averaged over the week prior to each respective timepoint). Incidence of adverse events (AEs) serious adverse events (SAEs), discontinuations because of AEs, and any treatment-related severe AEs.
Secondary	

 To evaluate the treatment effect of BOS-589 on defecation after 4 weeks, relative to PBO. To evaluate the treatment effect of BOS-589 on IBS-related signs and symptoms. To evaluate the steady-state pharmacokinetics of BOS-589. 	
 Change in stool consistency, measured by the daily Bristol Stool Form Score (BSFS) at Day 29 compared to baseline (averaged over the week prior to each respective timepoint). Change in stool frequency, measured by the total number of spontaneous bowel movements in 24 hours at Day 29 compared to baseline (averaged over the week prior to each respective timepoint). Change in the IBS Severity Score (IBS-SS) at Day 29 compared to baseline. Change in the IBS Global Scale (IBS-GS) at Day 29 compared to baseline (averaged over the week prior to each respective timepoint). Maximum observed plasma concentration (C_{max}); time to C_{max} (T_{max}); minimum plasma concentration (C_{min}); area under the concentration versus time curve (AUC) from time zero to 4 hours postdose (AUC_{0-4}); AUC from time zero to the last quantifiable concentration (AUC_{0-t}).

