6.5 Dose modification

Study treatment should be interrupted if the patient reports any treatment-related severe AE. Therapy should only be restarted after approval by the Medical Monitor.

If therapy is restarted, the same dose should be administered as that prior to occurrence of the AE. If the patient is still having tolerability issues and an AE reoccurs, the dose may be reduced from 2 tablets of study treatment bid to 1 tablet of study treatment bid, without breaking the study blind.

If another AE occurs after the study treatment dose reduction, study treatment will be permanently discontinued and the subject followed until the end of the study.

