9.2. Clinical Laboratory Evaluations

Laboratory tests identified in Appendix 1 in the protocol will be performed at times defined in the Schedule of Activities, Section 1.3 of the protocol. Clinical chemistry, hematology, and coagulation parameters will be reported based on the International System of Units (SI). All abnormal laboratory results will be evaluated by the Investigator as either clinically significant or not clinically significant.

Observed values and changes from baseline for hematology, clinical chemistry, urinalysis, and inflammatory biomarker laboratory evaluations will be summarized by cohort at each scheduled visit (Baseline/Day 1, Day 15, Day 29/Early Termination, and Day 43/End of Study) and most extreme change.

Box plots will be produced by visit and treatment for the recorded values of Erythrocyte Sedimentation Rate, C-reactive Protein, and Fecal Calprotectin. As well, line plots of the mean change from baseline of these three tests at each visit will be produced by treatment.

The number and percentage of patients experiencing treatment-emergent graded toxicities will be summarized by cohort and severity grade per the National Cancer Institute Common Terminology Criteria for Adverse Events (CTCAE) version 4.0.3. For each parameter, a patient will only be counted once using the worst-case value among all post-baseline timepoints. Laboratory toxicity will be summarized by incidence of CTCAE grade 3 and CTCAE grade 4 values for measures with a corresponding CTCAE grade. For measures without a corresponding CTCAE grade, incidence of 2.5 to < 5.0 X upper or lower limit of normal and ≥ 5.0 X upper or lower limit of normal cohort by cohort. Patients with missing values post-baseline will be excluded from the summary. The denominator for percentages will be the number of patients with at least one post-baseline assessment for the laboratory parameter being displayed. Separate summary counts will be prepared for parameters with bi-directional toxicity grading with “high/hyper” conditions depending on the maximum post-baseline value and the “low/hypo” conditions depending on the minimum post-baseline value.

All laboratory parameters will be provided in patient data listings for all enrolled patients.

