9.3. Other Safety Evaluations

For electrocardiogram and vital signs results, Marked Abnormality will be defined in the following sections. Should a patient have a Markedly Abnormal result at baseline, only those

Sponsor: Boston Pharmaceuticals, Inc.
Protocol Number: BOS-589-201
Version and Date: Version 1.2 12NOV2020

post-baseline results that are at least 1 grade more extreme than the baseline grade will be considered as a Marked Abnormality.

9.3.1. 12-Lead Electrocardiogram

12-lead electrocardiograms (ECGs) will be assessed as specified in the Schedule of Activities in Section 1.3 of the protocol. The following ECG parameters will be collected: PR interval (milliseconds [msec]), QRS interval (msec), QT interval (msec), QT interval corrected for heart rate (QTc) (msec), and Ventricular Rate (beats/min). ECG parameters and ECG evaluation will come directly from the database and will not be calculated during analysis.

Observed values and changes from baseline for ECG parameters will be summarized at each scheduled visit (Screening and Day 29/ Early Termination) by cohort and overall.

Observed and change from baseline values on Day 29 in QTc status categorized as markedly abnormal (defined in the table below) or not will be summarized.

QTc Measure	Markedly Abnormal Criteria
Observed	450–480 msec, inclusive [CTCAE grade 1] 481–500 msec, inclusive [CTCAE grade 2] > 500 msec [CTCAE grade 3 or higher]
Change from Baseline	31–60 msec, inclusive, increase from baseline >60 msec increase from baseline

If triplicate measures were taken at a single time point, the average will be summarized. All ECG data will be presented in a by patient data listing for all enrolled patients. Measures meeting the markedly abnormal criteria will be flagged in the listing.

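### A symptom-free laboratory or ECG adverse event fits only the mild category, whatever its size, so it adds nothing to the related severe AE component of the primary safety endpoint

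*Protocol*

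**What the plan says.** Protocol 8.5.4.1 requires the investigator to put every AE and SAE into one of three categories. The lowest is "Mild: An event that is easily tolerated by the patient, causing minimal discomfort and not interfering with everyday activities". The middle one needs discomfort together with interference in daily life. The highest is "Severe: An event that prevents normal everyday activities". None of them refers to the size of a measured deviation, to medical risk or to a need for treatment.

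Measured findings do enter the AE record. Protocol 8.5.1 lets an abnormal laboratory result be an AE. Protocol 8.4.5 tells the investigator to "record in the AE section of the CRF any clinically relevant changes occurring during the study", and Protocol 8.4.4 states: "Any clinically significant change in ECG interpretation will be recorded as an AE".

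The primary safety endpoint (Protocol 3, repeated in SAP 2) has four parts: incidence of AEs, incidence of SAEs, and then "discontinuations because of AEs, and any treatment-related severe AEs".

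SAP 9.1 keeps the mild, moderate and severe levels for AEs. It tabulates moderate or severe treatment-emergent events, both overall and related, and all such events by severity. CTCAE grades appear elsewhere. SAP 9.2 summarises laboratory values by "severity grade per the National Cancer Institute Common Terminology Criteria for Adverse Events (CTCAE) version 4.0.3", and SAP 9.3.1 bands QTc, with the top band given as "> 500 msec [CTCAE grade 3 or higher".

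The word severe also drives a conduct rule in Protocol 6.5: "Study treatment should be interrupted if the patient reports any treatment-related severe AE".

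**The concern.** Laboratory and ECG abnormalities often cause no symptoms. A scale built on how the patient feels and functions has no means of ranking them. If the only category such an AE can meet is the lowest, the related severe AE component is blind to this kind of toxicity by construction, in every arm. A count of zero would then say nothing about it.

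The outputs would also disagree with each other. The same finding could stand in the highest band of the ECG table and as a mild event in the AE tables, with nothing in the SAP to explain the difference.

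**Working it through.** The plan states no figure on this point and no arithmetic is needed. The check is to take one case through the definitions. The case is constructed for illustration: a QTc of 510 msec without symptoms, judged clinically significant and related to study drug.

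1. **Is it an AE?** Yes, under Protocol 8.4.4.
2. **Which category does it meet?** Severe requires that daily activities be prevented; they are not. Moderate requires discomfort and interference; there is neither. Mild is the only definition it satisfies. The same answer follows for any size of deviation, because size is not a criterion.
3. **Does any other text give AE severity a different basis?** Protocol 8.5.4.1 describes severity as a rating of intensity but supplies no criterion for a finding without symptoms. SAP 9.1 repeats the three levels. Its rule that a missing severity is set to severe does not touch an event already rated mild. SAP 9.2 and 9.3.1 grade measured values, and nothing carries those grades over to the AE record.
4. **Where is the event counted?**

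| Output | Counted? |
|---|---|
| Any TEAE; related TEAE (SAP 9.1) | Yes |
| SAE, or discontinuation because of an AE | Only if it meets those definitions |
| Moderate or severe TEAE, overall or related (SAP 9.1) | No |
| TEAEs by severity (SAP 9.1) | Yes, as mild |
| Related severe AE component (Protocol 3, SAP 2) | No |
| QTc categories (SAP 9.3.1) | Yes, in the highest band |

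If *k* such events occur, their contribution to the related severe component is *k* × 0 = 0, whatever *k* is.

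5. **Does the component have its own table?** No. SAP 9.1 lists moderate and severe related events pooled, and all events by severity regardless of relatedness. No listed table isolates events that are both severe and related.

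**The case against.** The strongest reply is that this is a deliberate separation. Protocol 8.5.4.1 treats severity as intensity, and medical importance is left to seriousness under Protocol 8.5.3. Three of the four safety components can still count a symptom-free finding. SAP 9.2 tabulates grade 3 and grade 4 laboratory values by cohort on the worst post-baseline value, and SAP 9.3.1 tabulates QTc bands. In a randomised placebo-controlled trial, comparing arms on those tables does not need the investigator's view of causality. Protocol 2.2.3.2 also reports no drug-related clinically significant laboratory or ECG changes at up to 200 mg bid for 14 days, so few such events may occur.

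Most of that stands, and it limits the harm. It does not give the named component a way to count these events. The seriousness route does not repair it either: 8.5.4.1 keeps serious and severe apart, so an event could be an SAE and still be rated mild.

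A reader might go further and infer that a dangerous symptom-free finding, such as a blood-count abnormality, could not lead to treatment being stopped because Protocol 6.5 turns on the word severe. The documents do not support that. Protocol 8.5.3 says important medical events should usually be considered serious and names blood dyscrasias among its examples. Protocol 7.2 suspends treatment for any drug-related SAE and has its own liver criteria. Protocol 7.1 leaves management of any clinically significant finding to the investigator.

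A reader might also infer that an ALT meeting a 7.2 criterion would be grade 3 in the SAP laboratory table. Neither document prints a CTCAE limit for ALT, so only the QTc conflict can be shown from the text.

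**Conclusion.** The point holds in a confined form. On the definitions as written, a symptom-free laboratory or ECG AE fits only the mild category. It is therefore absent from one of the four primary safety components and from the SAP tables of moderate or severe events. For QTc above 500 msec, the SAP's own ECG table contradicts the AE grading.

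This rests on investigators applying the definitions literally. Some may read intensity more broadly and grade such an event higher. With up to 66 sites and no criterion for these cases, that would make the component inconsistent between sites rather than correct.

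The size in patients cannot be stated. The documents give no expected rate of such events, and any count chosen for illustration would be an assumption. A reader might infer that this toxicity would be missing from the study report; it would not be, because it remains in AE incidence, in the SAP 9.2 and 9.3.1 tables and in the listings. What is affected is the meaning of a low or zero related severe count.

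**What to change.** Change the analysis, not the investigator's scale. In SAP 9.1, for AEs that are laboratory or QTc findings, derive a second severity as the worse of the investigator's category and the grade on the CTCAE version the SAP already names (grade 1 = mild, 2 = moderate, 3 or higher = severe). Report the related severe and the moderate or severe counts on this basis next to the counts by investigator category. Where a laboratory measure has no CTCAE grade, keep the investigator's category. Add a table of severe related TEAEs, so that the named component has an output of its own. Record the addition in SAP 3.2.

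The cost is a paragraph in the SAP, one more table, and programming to link AE records to the underlying values and to derive grades 1 and 2, since the SAP 9.2 table is limited to grades 3 and 4. The severe count may look a little less favourable.

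Redefining severe in Protocol 8.5.4.1 itself would be a different step, because through Protocol 6.5 it would also change when treatment is interrupted. Separately, the sponsor must reconcile 6.5 (keyed to severe AEs), 7.2 (keyed partly to laboratory criteria) and 8.5.4.1. No interruption threshold is proposed here.

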8.5.4.2 Assessment of Causality

All AEs must have their relationship to the investigational product and/or study participation assessed by the Investigator who examines and evaluates the patient based on temporal relationship and his or her clinical judgment. Alternative causes, such as underlying disease, concomitant therapy, and other risk factors, as well as the temporal relationship of the event to investigational product administration will be considered and investigated. The Investigator will also consult the IB in his or her assessment.

The degree of certainty about causality will be graded using the categories below:

- **Related** – The AE is known to occur with the investigational product, there is a reasonable possibility that the investigational product caused the AE, or there is a temporal relationship between the investigational product and event. Reasonable possibility means that there is evidence to suggest a causal relationship between the investigational product and the AE.
- **Not Related** – There is not a reasonable possibility that the administration of the investigational product caused the event, there is no temporal relationship between the investigational product and event onset, or an alternate etiology has been established.

For each AE, the Investigator must document in the medical notes that he or she has reviewed the event and has provided an assessment of causality. The Investigator may change his or her opinion of causality in light of follow-up information and updated causality assessment reported.

